5.1 Nonclinical Studies

5.2 Clinical Studies

Results of the three completed Phase 1 studies (MT-7117-E01, MT-7117-E02, and MT-7117-E03) conducted with MT-7117 can be found in the Investigator's Brochure.¹¹

Study MT-7117-A01

A Phase 2, randomized, double-blind, placebo-controlled study to assess the efficacy, tolerability, and safety of MT-7117 in subjects with EPP or XLP has been completed. Top-line

data was received on October 25, 2019 from a total of 102 randomized subjects (2 active groups at [REDACTED] or [REDACTED] doses and 1 placebo group with 33, 34, and 35 subjects in each treatment group, respectively). The efficacy results at Week 16 showed an improvement in average daily time (minutes) to first prodromal symptom, which was greater than the placebo for the [REDACTED] (p<0.008) and [REDACTED] (p<0.003) arms, respectively. In the [REDACTED] and [REDACTED] arms, the primary endpoint of time-to-prodrome for MT-7117 versus placebo was > 50 minutes, irrespective of the season of the year. The improvement of time-to-prodrome (primary endpoint) and the duration of sunlight exposure (secondary endpoint) were observed as early as Week 6. Dose-related increase in pigmentation was observed. Treatment-emergent adverse event (TEAE)s leading to discontinuation in the [REDACTED] arm were higher than the placebo (14.3% vs. 0%). TEAEs were observed in System Organ Class (SOC) of nervous system disorders, gastrointestinal disorders, skin and subcutaneous disorders, and general disorders. There was no trend in hepatic adverse event (AE)s, and no trend of clinically significant changes in Liver Function Test (LFT)s were observed. A treatment-emergent serious adverse event (SAE) occurred in one subject (anaphylactic reaction) in the MT-7117 [REDACTED] arm and was unrelated to treatment.

Study MT-7117-A02

A Phase 1 open-label, single-center, parallel-group study to assess the pharmacokinetics, safety, and tolerability of a single dose of MT-7117 in healthy volunteers with normal hepatic function, moderately impaired hepatic function, and mildly impaired hepatic function, is ongoing. Up to 24 subjects are planned to be in this study (8 subjects in each treatment group).

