7.4 Rationale for Dose Selection

The current Phase 3 study will investigate the efficacy and safety of MT-7117 in subjects with EPP or XLP. In the MT-7117-E01 human healthy volunteer study, single doses up to [REDACTED]

[REDACTED] in healthy female subjects have been shown to be safe. Some reversible increases in skin pigmentation, consistent with the expected pharmacology, were noted following repeat dosing and appeared to show a dose-related trend. No SAEs occurred during Study MT-7117-E01. In the MT-7117-A01 Phase 2 study of MT-7117 in 102 subjects with EPP or XLP, both [REDACTED] and [REDACTED] MT-7117 were associated with greater improvement compared to placebo in average daily time to prodromal symptoms at Week 16. During the 16 weeks dosing and 6 weeks follow up, there were no major safety concerns with the doses of [REDACTED] and [REDACTED] MT-7117. One SAE of anaphylaxis was observed during the study. The event causality was considered not reasonably possible in relation to the investigational drug due an identified food reaction. It was noted MT-7117 [REDACTED] group had a higher incidence of TEAEs, severe TEAEs, TEAEs causing discontinuations compared to MT-7117 [REDACTED], which were primarily driven due to hyperpigmentation events, headache, nausea, vomiting, and diarrhea. Additional details can be found in the Investigator's Brochure.¹¹

A population PK model was developed from the adult data in Studies MT-7117-E01 and MT-7117-A01. Steady-state Maximum observed plasma concentration (C_{max}) and Area under the plasma concentration-time curve from time zero to 24 hours (AUC₀₋₂₄), which were calculated from individual post-hoc parameters of 124 subjects using population PK model, were used to develop a target range for exposures in the pediatric population. The adult population PK model was then used to simulate the expected exposures in pediatric patients from ≥ 12 to ≤ 17 years

of age. [REDACTED]

[REDACTED] In summary, based on available clinical MT-7117 data, it is considered most likely that either [REDACTED] or [REDACTED] will demonstrate a suitable efficacy/safety profile.

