10.9.4 Nevi Evaluation

Nevi will be assessed at the specified timepoints shown in the schedule of assessments (Table 9-1). Baseline nevi evaluation will be conducted at any time (Visit 1 or 2) before randomization.

Nevi will be assessed locally by a visual full body examination performed by a dermatologist or other qualified site staff. Any subject with suspicious nevi of clinical concern will have treatment temporarily discontinued and be referred for further nevi evaluation (e.g., biopsy), as deemed necessary by the dermatologist or other qualified site staff.

Any biopsy samples collected during the study will be sent for evaluation to the central pathology lab. If there are any clinically significant adverse findings from the biopsy, subjects will not be allowed to resume study drug and will be discontinued from study treatment. Adverse change must be demonstrated histologically and confirmed by central pathologist. Visual evaluation of change will not be acceptable criteria for complete discharge from treatment. If central assessment determines that lesion or nevi is benign, and the findings are not clinically significant, subject will be allowed to resume study treatment at the same dose when study drug was interrupted. Clinical sites will have access to a centralized dermatology specialist with experience on nevi. The centralized dermatology specialist will be available to communicate with the Investigator, dermatologist and/or qualified staff on the changes of any expected potential changes in nevi and advice on the process management prior and after biopsy.

The results will be recorded in the source documents and the eCRF as well as shared and discussed with the subject. Nevi of clinical concern must be recorded as AE.

Nevi assessment details will be fully described in a separate document.

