H7: There is no treatment difference between MT-7117 [REDACTED] and placebo in change from baseline for total score in the domain of pain intensity in the PROMIS-57 at Week 26.

H8: There is no treatment difference between MT-7117 [REDACTED] and placebo in change from baseline for total score in the domain of pain intensity in the PROMIS-57 at Week 26.

H9: There is no treatment difference between MT-7117 [REDACTED] and placebo in the percentage of subjects who are responders at Week 26 based on average daily sunlight exposure time to first prodromal symptoms using the within-subject meaningful change of 66 minutes increase.

H10: There is no treatment difference between MT-7117 [REDACTED] and placebo in the percentage of subjects who are responders at Week 26 based on average daily sunlight exposure time to first prodromal symptoms using the within-subject meaningful change of 66 minutes increase.

H11: There is no treatment difference between MT-7117 [REDACTED] and placebo in change from baseline for total score in the domain of physical function in the PROMIS-57 at Week 26.

H12: There is no treatment difference between MT-7117 [REDACTED] and placebo in change from baseline for total score in the domain of physical function in the PROMIS-57 at Week 26.

Subgroup Analysis

The consistency of treatment effect on the primary endpoint across different subgroups will be explored based on the ITT population and the primary estimand for age category, [REDACTED] [REDACTED] Country and Race (as entered in the eCRF) etc. This subgroup analysis method will be prospectively defined in Primary Week 26 SAP. This analysis is exploratory and the results from this analysis will not affect the choice of terms used in the model for the primary analysis.

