2.2 Estimand

2.2.1 Primary estimand

The primary estimand construction elements for this study are:

- Population: All randomized subjects who received at least 1 dose of study medication with baseline and post-randomization sunlight exposure diary assessment.
- Variable: Change from baseline in average daily sunlight exposure time (minutes) to first prodromal symptom associated with sunlight exposure between 1 hour post sunrise and 1 hour pre-sunset at Week 26 (Visit 7).
- Inter-current event of treatment discontinuation using treatment policy: Regardless of early discontinuation of study drug due to any reason until the end of the double-blind treatment period.
- Population-level summary: Absolute mean difference in change from baseline in average daily sunlight exposure time (minutes) to first prodromal symptom between MT-7117 and placebo groups.

The primary estimand will be based on effectiveness assumption (de-facto) using treatment policy: The treatment effect will be attributable to the subject's initially randomized treatment regardless of treatment discontinuation.

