H10: There is no treatment difference between MT-7117 [REDACTED] and placebo in the percentage of subjects who are responders at Week 26 based on average daily sunlight exposure time to first prodromal symptoms using the within-subject meaningful change of 66 minutes increase.

H11: There is no treatment difference between MT-7117 [REDACTED] and placebo in change from

baseline for total score in the domain of physical function in the PROMIS-57 at Week 26.

H12: There is no treatment difference between MT-7117 [REDACTED] and placebo in change from baseline for total score in the domain of physical function in the PROMIS-57 at Week 26.

Subgroup Analysis

The consistency of treatment effect on the primary endpoint across different subgroups will be explored based on the ITT1 population and the primary estimand for the following subgroups using the primary efficacy analysis.

- Gender (Male, Female)
- Age group (age <18, 18=< age)
[REDACTED]
- Ethnicity (Hispanic or Latino, Non-Hispanic or Latino, Others)
- Race (White, Black or African American, Asian(Japanese), Others)
- BMI (BMI <30, BMI \geq 30 kg/m²)
[REDACTED]
[REDACTED]
- Seasonality1 (Randomized in Spring and Summer inclusive, Other)
- Seasonality2 (Week 26 visit in Spring and Summer inclusive, Other)
- Average melanin density at BL (>=Median, <Median)
- Fitzpatrick scale test category (I-II or III-VI)
- Protoporphyrin (>=Median, <Median)
- Porphyrin (>=Median, <Median)
- EPP vs XLP
[REDACTED]
[REDACTED]
[REDACTED]
[REDACTED]
[REDACTED]
- Study Drug Compliance by Week 26 (no study drug suspension, any suspension or permanent study drug discontinuation)

Bayesian analysis for adult and adolescent subgroups

Age group (age <18, 18=<age)

In order to estimate treatment effects for adult and adolescent for the primary endpoint, Bayesian subgroup hierarchical model and Commensurate prior model will be performed using both adolescent and adult subgroup data in order to get greater precision on treatment effect

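### SAP 8.2.1 compares each dose with placebo within subgroups formed by interrupting or stopping drug after randomisation, so these exploratory contrasts are not randomised comparisons

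*SAP*

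**What the plan says.** The Subgroup Analysis part of SAP 8.2.1 opens: "The consistency of treatment effect on the primary endpoint across different subgroups will be explored based on the ITT1 population and the primary estimand". It says the primary efficacy analysis will be used, and that analysis yields a difference from placebo for each dose with a 95% CI and p-value. The last visible factor in the list is "Study Drug Compliance by Week 26 (no study drug suspension, any suspension or permanent study drug discontinuation").

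The estimand under which this is done is set out in SAP 2.2.1. Discontinuation is handled by treatment policy: "Regardless of early discontinuation of study drug due to any reason until the end of the double-blind treatment period". The same section adds: "The treatment effect will be attributable to the subject's initially randomized treatment regardless of treatment discontinuation".

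Protocol 14.3.2.1 limits the weight of all the subgroup work: "This analysis is exploratory and the results from this analysis will not affect the choice of terms used" in the primary model.

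The protocol also shows that stopping can depend on treatment:
- Section 5.2 reports that in Phase 2 the TEAEs leading to discontinuation in one (redacted) "arm were higher than the placebo (14.3% vs. 0"%).
- Section 7.4 says one dose "group had a higher incidence of TEAEs, severe TEAEs, TEAEs causing discontinuations compared to MT-7117" at the other dose.
- Section 10.9.4 gives a route to temporary interruption: "Any subject with suspicious nevi of clinical concern will have treatment temporarily discontinued".
- Section 12.3.1 allows dosing to be suspended after a hepatic AESI.

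No visible text in SAP 8.2.1 adds a caveat, an adjustment or a principal-stratum method for this factor.

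**The concern.** A subgroup analysis keeps the protection of randomisation when subjects are classified by something fixed before treatment starts. Whether a subject interrupts or stops drug is partly a result of the arm. Active subjects who stayed on drug without a break have been filtered by tolerability. Placebo subjects who did so have been filtered differently, or hardly at all. The two groups need not be alike in the outcome they would have had on the same treatment.

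There is also a mismatch with the estimand. An effect defined regardless of discontinuation cannot be shown to be consistent by dividing subjects according to discontinuation.

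What is at stake is interpretation. The output would sit beside valid baseline subgroups, with an interval and a p-value. It could suggest that the drug works better in those who keep taking it, or that the doses differ, when some or all of the pattern is selection.

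**Working it through.** **The plan's own figures.** These are not in dispute and supply the inputs. SAP 3.3 gives an SD of 79.3 min and differences of 57 and 52 min, so the effect sizes are 57/79.3 = 0.72 and 52/79.3 = 0.66. With 42 completers per arm, the normal approximation gives 90.9% power for 57 min (stated: 91%). The chance that both comparisons succeed in fixed sequence with a shared placebo arm is 79.0% by simulation (stated: 79%). 42/0.80 = 52.5, rounded up to 53; 53 x 3 = 159, as stated.

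**Other inputs.** About 61 subjects per arm (Protocol 8.1). Phase 2 TEAE discontinuation of 14.3% versus 0% (Protocol 5.2). The correlation rho between outcome and the tendency to stop is not in the documents, so it is assumed and varied.

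**Model.** Suppose the true effect is zero and subjects with poorer outcomes tend to stop, with correlation rho. If a proportion p stops, the mean among those who continue is shifted by

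shift = rho x SD x phi(z_p)/(1 - p),

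where z_p is the normal quantile of p and phi the normal density. The false difference is the active shift minus the placebo shift.

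**14.3% versus 0%.** z = -1.067, phi = 0.2258, and 0.2258/0.857 = 0.2635. Multiplying by 79.3 gives 20.9 min at rho = 1, which is the upper bound. The placebo shift is 0.

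| rho | false difference, uninterrupted subgroup |
|---|---|
| 0 | 0 |
| 0.2 | 4.2 min |
| 0.3 | 6.3 min |
| 0.5 | 10.4 min |

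Direct simulation gives 6.3 min at rho 0.3 and 10.3 min at rho 0.5. A nominal 5% t-test in this subgroup, starting from 61 per arm, rejects in about 6.9% of trials at rho 0.3 and 11.0% at rho 0.5.

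**14.3% versus 5%.** The placebo term is 0.1031/0.95 x 79.3 = 8.6 min, so the multiplier is 20.9 - 8.6 = 12.3 min. The false difference is 3.7 min (rho 0.3) to 6.1 min (rho 0.5).

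**Equal rates and equal selection in each arm.** The false difference is 0.

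**The interrupted-or-stopped subgroup.** 14.3% of 61 is 8.7, so about 9 active subjects. If placebo stopping were 0% there would be no comparator. If it tracked the planned 20% dropout, there would be 0.20 x 61, about 12 placebo subjects. An unstructured covariance over 13 visits has 13 x 14/2 = 91 parameters, which groups of this size could not support.

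**The case against.** The strongest reply is that little depends on this. The analysis is exploratory, it cannot alter the primary model, and full-arm comparisons are reported under both estimands. The contrast is also imprecise: with about 52 against 61 subjects its standard error is 79.3 x sqrt(1/52 + 1/61), about 15 min, so a bias of 4 to 6 min lies well inside the noise. All of this stands, and it sets the weight of the point. It does not make the contrast interpretable.

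Several stronger readings are tempting, and the documents do not support them.

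- **That the bias is 0.143 x 57, about 8 min.** This sets the gap between continuers and stoppers equal to the planned drug effect. If stoppers merely lose that effect and are otherwise comparable, the 8 min is dilution of the treatment-policy mean and not selection.
- **That the bias must flatter the drug.** Protocol 7.4 names hyperpigmentation among the main drivers of the excess TEAEs and discontinuations, and treats pigmentation as expected pharmacology. Subjects stopping for that reason could be better responders, which would push the uninterrupted estimate down.
- **That stopping is dose-related.** Dose labels are redacted. A difference between dose groups is visible, but not which dose was higher.
- **That the placebo cell will be empty and the model cannot be fitted.** The 14.3% versus 0% covers only TEAE discontinuation in Phase 2, whereas the SAP factor covers every reason and includes temporary interruption. SAP 8.2.1 also names four simpler covariance structures if the unstructured one fails. These may help a small cell to converge, but they cannot supply a missing comparator.
- **That this is the only post-randomisation factor in the list.** Some lines are redacted. The second seasonality factor uses the Week 26 visit date, although that is largely fixed by the randomisation date.

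The SAP also does not say whether the model is refitted in each subgroup or extended with interaction terms. The fault is the same either way, because both compare arms conditional on a consequence of treatment.

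**Conclusion.** The point holds as a minor one. Contrasts of active against placebo within groups defined by interruption or discontinuation up to Week 26 are not randomised comparisons, and they do not address consistency of a treatment-policy effect. That conclusion needs only that treatment can affect stopping, which the protocol's Phase 2 results and its own interruption triggers make plausible.

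Neither the size nor the sign of the bias in this trial can be derived from the documents. The range of about 4 to 10 min is an illustration. It rests on a zero true effect, SD 79.3 min, 14.3% versus 0% stopping, poorer outcomes among stoppers, and rho of 0.2 to 0.5. The contrast in the interrupted-or-stopped subgroup may be very imprecise, and is not estimable only if a cell is empty.

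A reader might infer that the confirmatory result is at risk. It is not: H1 to H12, the primary MMRM and the type I error control do not use this factor.

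**What to change.** Remove the study drug compliance factor from the treatment-effect subgroup list in SAP 8.2.1. In its place:

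- Report interruption and permanent discontinuation by arm, as SAP 8.1.9 already plans, and the reasons for discontinuation, which are planned in SAP 8.1.1.
- Show the primary endpoint by interruption status within each arm as descriptive statistics only, with no between-arm differences, intervals or p-values. Add a note that these groups were not formed by randomisation, since means printed side by side still invite comparison.
- For the effect had subjects not discontinued, refer to the secondary estimand (SAP 2.2.2 and the supportive analysis in 8.2.1). It addresses permanent discontinuation but not temporary interruption. If the effect without interruption is of interest, it needs its own estimand with stated assumptions.

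The basic cost is one line of SAP wording and slightly less analysis work. The downside is the loss of one exploratory contrast.

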3.3 Sample Size and Power Considerations

For the primary estimand, the sample size of 159 is expected to provide adequate power for the comparisons between MT-7117 and placebo for change from baseline in the average daily sunlight exposure time (minutes) to first prodromal symptom associated with sunlight exposure between 1 hour post sunrise and 1 hour pre-sunset at Week 26 based on the MT-7117-A01 study. The calculation of sample size assumes a 2-sided alpha level of 0.05 and a 20% dropout rate up to Week 26. The sample size of 42 completers per treatment group will provide 91% and 79% power to detect an effect size of 0.72 and 0.66 in the average daily time (minutes) to first prodromal symptom associated with sunlight exposure between 1 hour post sunrise and 1 hour pre-sunset at Week 26 (ie, an absolute treatment difference of 57 mins between MT-7117 [REDACTED] [REDACTED] vs placebo, 52 mins between MT-7117 [REDACTED] [REDACTED] vs placebo, and a standard deviation [SD] of 79.3 mins). The sample size of 42 completers was calculated by SAS simulation using the fixed sequence testing procedure in order to confirm the power affected by multiplicity adjustment in treatment comparison for primary endpoint. Taking into account for a 20% dropout rate up to Week 26, total sample size of 159 was calculated.

Due to the rapid enrollment rate in the last few months of the enrollment period after COVID-

19 restrictions were lifted in many countries, a total of 184 subjects were enrolled.

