and address random high and random low data values due to small sample estimates. This means these analysis does not estimate treatment effect within adolescent subgroup in isolation of adult subgroup. Details of the model and the framework can be found in Appendix 1. The posterior means, SE and 95% Credible Interval(CrI) for the primary endpoint will be presented for each treatment group. The posterior mean, SE and 95% CrI will be obtained for the difference of each of the active MT-7117 treatment groups versus placebo. In addition, the probability that the difference in the primary endpoint versus placebo > 0 will be presented for MT-7117 [REDACTED] and [REDACTED], respectively. If this probability is at least greater than 95%, then this will be considered as “a statistically significant difference” for the active dose and the subgroup. If the posterior mean for the difference in the primary endpoint versus placebo will be greater than 0 in both adult and adolescent subgroups in the MT-7117 active dose, then this will be considered as “a positive trend” for the active dose among the subgroups.

Funnel plot analysis

In order to confirm the relation between change from baseline for the average potential outliers of treatment effect by site and by country for the primary endpoint, funnel plot analysis by site and by country will be performed respectively. The curves on the graph delineate overall mean treatment difference (MT-7117 [REDACTED] – Placebo, MT-7117 [REDACTED] – Placebo) plus/minus 2*standard error limits [$Z(0.05/2) \times$ overall standard deviation (SD) $\times \text{sqrt}(2/n)$, Note: $Z(0.05/2) = \text{quantile}("Normal", 0.975)$]. Overall SD will be SD for overall in the calculated two treatment groups and n will be determined (e.g. 1 to 15) based on average sample size per treatment group in the calculated two treatment groups in each site and each country.

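### The age-subgroup 'positive trend' label would be earned in more than half of trials with no adolescent effect, provided the drug works in adults as planned

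*SAP*

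**What the plan says.** Under its Bayesian heading, SAP 8.2.1 states that a "Bayesian subgroup hierarchical model and Commensurate prior model will be performed using both adolescent and adult subgroup data". It warns that "these analysis does not estimate treatment effect within adolescent subgroup in isolation of adult subgroup". For each dose it will report posterior means, SEs, 95% credible intervals and the probability that the difference from placebo is above zero.

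Two labels follow. The stricter one is a claim of statistical significance for a dose and subgroup: "If this probability is at least greater than 95%, then this will be considered as" significant. The weaker one calls the dose a positive trend among the subgroups: "If the posterior mean for the difference in the primary endpoint versus placebo will be greater than 0 in both adult and adolescent subgroups". The readable text attaches no probability, effect size or own-data condition to the weaker label. On the models it says "Details of the model and the framework can be found in Appendix 1", and that appendix is not readable in the supplied text.

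Separately, the subgroup list in the same section includes "Age group (age <18, 18=< age"), to be analysed with the primary efficacy model. Protocol 14.3.2.1 calls the subgroup analysis exploratory. Neither Bayesian label is among H1 to H12.

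**The concern.** With a normal posterior, a mean above zero is the same as a posterior probability above 50%. A sign-only rule of that kind is passed half the time by an estimate centred on zero, before any borrowing. Borrowing then moves the adolescent mean toward the adult mean. If adults respond, a null adolescent effect passes more often still.

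The indication in the protocol synopsis covers adolescents, and Protocol section 5 stresses that paediatric patients have no approved treatment. A pre-specified favourable label spanning both age groups could therefore be read as support for an effect in adolescents, when much of what earned it may be the adult result.

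**Working it through.** **Reproducing the plan's figures.** SAP 3.3: "The calculation of sample size assumes a 2-sided alpha level of 0.05 and a 20% dropout rate up to" Week 26. The other inputs there are differences of 57 and 52 min, SD 79.3 and 42 completers per arm.
- Effect sizes: 57/79.3 = 0.72 and 52/79.3 = 0.66, as stated.
- Power for the first dose: 90.9% (stated 91%).
- Power to pass both steps of the sequence: 78.9% by simulated t-tests, or 80.0% by bivariate normal with correlation 0.5 (stated 79%).
- Size: 42/0.8 = 52.5, rounded up to 53 per arm; 3 × 53 = 159, as stated.

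The planning inputs can therefore be relied on. The readable text gives no operating characteristics for the Bayesian rule, so there is no figure of that kind to reproduce.

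**Model.** Two subgroup effects are drawn from N(μ, τ²) with flat μ, and each subgroup estimate has variance v = 2 × 79.3²/n. Then:
- adolescent posterior mean = w·y_adol + (1 − w)·y_adult
- w = (v_adult + 2τ²)/(v_adult + 2τ² + v_adol)

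A commensurate prior has the same form. Assumptions: τ held fixed, 50 adults per arm, 4 or 10 adolescents per arm, equal SD and equal allocation.

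**Variances.** 2 × 79.3² = 12,577. So v_adult = 12,577/50 = 251.5, and v_adol = 3,144.2 (n = 4) or 1,257.7 (n = 10).

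**Adult condition.** Without borrowing, Φ(57/√251.5) = 99.98% and Φ(52/√251.5) = 99.95%. The adolescent mean decides the label.

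**Two worked cases**, true adolescent effect 0, adults 57 min:
- τ = 50, n = 4: w = 5,251.5/8,395.8 = 0.6255. Expected adolescent posterior mean = 0.3745 × 57 = 21.3. Its SD = √(0.6255² × 3,144.2 + 0.3745² × 251.5) = 35.6. Φ(21.3/35.6) = 72.6%.
- τ = 20, n = 10: w = 1,051.5/2,309.2 = 0.4554. Expected mean = 31.0, SD = 18.3. Φ(31.0/18.3) = 95.5%.

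**Share of trials with both posterior means above 0, adolescent effect 0:**

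| τ (min) | 57 min, n=4 | 57 min, n=10 | 52 min, n=4 | 52 min, n=10 |
|---|---|---|---|---|
| 10 | 99.9% | 99.7% | 99.8% | 99.5% |
| 20 | 99.0% | 95.5% | 98.3% | 93.9% |
| 50 | 72.6% | 64.9% | 70.8% | 63.6% |
| 80 | 59.6% | 56.1% | 58.8% | 55.6% |
| 160 | 52.5% | 51.6% | 52.2% | 51.4% |
| no borrowing | 50.0% | 50.0% | 50.0% | 50.0% |

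**Other assumptions.** With 49 evaluable per arm in total (184/3 ≈ 61, less 20%) and 3 to 12 adolescents among them, fixed τ gives 90% to 99% at 20, 68% to 85% at 40, 55% to 61% at 79.3, and 51% to 53% at 160. With τ estimated, under half-normal priors (scale 20 to 160) or a half-Cauchy prior (scale 40), the range is about 63% to 98%.

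**Drug works in neither group.** The label is met in 25% of trials per dose with no borrowing (0.5 × 0.5), rising to 50% with full pooling.

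**The stricter 95% label**, for a null adolescent effect with adults as planned and τ estimated as above: met in about 7% to 43% of trials.

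**What the label can tell a reader.** If it appears in at least half of trials with no adolescent effect, and at most all trials with one, its likelihood ratio is at most 1/0.5 = 2.

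**The case against.** The strongest defence is that this is a descriptive label in an exploratory analysis. It carries no alpha and triggers no decision in the readable text. Its wording refers to a dose among the subgroups, so it can be read as saying only that the direction agrees. The SAP itself warns that the adolescent effect is not estimated on its own, provides a stricter label, and already plans the posterior probability, the credible interval and an age-subgroup analysis. The amount of borrowing is set in an appendix that cannot be read here and may give operating characteristics.

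Most of this stands, and it limits the point to how adolescent results are described. A reader might go further and infer that the rule hardly ever fails, that it simply retests the adults, or that it is the only planned evidence on adolescents. The documents do not support those readings. At τ of 50 to 80 min with adults at 57 min, the label fails in 27% to 44% of null trials. Near-certain passing needs strong borrowing, which cannot be confirmed. The age-subgroup analysis is planned separately. A negative adolescent posterior mean despite borrowing from responding adults would also be informative.

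The defence does not remove the central result. Even very weak borrowing brings the rate down only to just over 50%.

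**Conclusion.** The point holds in a conditional form. If the drug works in adults as planned and does nothing in adolescents, the label is earned in more than half of trials under any positive borrowing, apart from a loss of less than 0.1 percentage point from the adult condition. The direction does not depend on the unseen prior, but the size does. With 4 to 10 adolescents per arm, it runs from just over 50%, through about 56% to 73% (τ 50 to 80), to 95% to 100% at 57 min or 94% to 100% at 52 min (τ 10 to 20). If adults do not respond either, it is about 25% to 50% per dose, so the rule is not usually met in every null scenario.

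Seeing the label at most doubles the odds of an adolescent effect, and adds almost nothing under strong borrowing. It cannot be taken as evidence of one. A reader might also infer inflation of the trial's error rate; that does not follow, because the label is outside H1 to H12.

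The adolescent numbers and τ are assumptions. Protocol 11.5 also gives one redacted subgroup a 1:2 allocation, which could change adolescent numbers per arm but not the direction.

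**What to change.** Remove the 'positive trend' label from SAP 8.2.1. Describe adolescents by the posterior probability that the difference exceeds zero and its 95% credible interval, both already planned. Show them in the same table as the adolescent-only estimate and interval from the age-subgroup analysis, so that the contribution of borrowing is visible.

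If any label is kept, state its false-label rate at zero adolescent effect, with adults at the planned effect, under the pre-specified prior of each of the two models.

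The cost is a few lines of SAP wording and one small simulation, and a favourable descriptive label is lost. Data collection, the primary analysis and the testing sequence do not change.

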6.2 Statistical Tests

Unless otherwise specified, all formal statistical tests of treatment effects will be done at two-sided significance level of 0.05. Point estimates will be accompanied with two-sided 95% CIs where applicable.

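### The funnel-plot limits use the arithmetic average arm size, so for a given SD they are too narrow for a site or country with clearly unequal arms; the SD to be used is also not defined

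*SAP*

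**What the plan says.** The funnel plot paragraph of SAP 8.2.1 plans one plot by site and one by country, to look for "potential outliers of treatment effect by site and by country for the primary endpoint". The curves are the overall mean difference between a dose and placebo "plus/minus 2*standard error limits", with the half-width spelled out as the 97.5% normal quantile × overall SD × sqrt(2/n).

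Two inputs are then described:

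- **n:** "n will be determined (e.g. 1 to 15) based on average sample size per treatment group in the calculated two treatment groups", taken for each site and each country.
- **SD:** "Overall SD will be SD for overall in the calculated two treatment groups". The text does not say whether this is pooled within arm or computed on all subjects of both groups together.

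No rule follows for a point outside the curves: no test, exclusion or action.

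**The concern.** The curves are labelled as standard error limits. The standard error of a difference between two means is SD × sqrt(1/n1 + 1/n2), which equals SD × sqrt(2/n) only if n is the harmonic mean of the two arm sizes. The arithmetic average is larger whenever the arms differ, so the curve is drawn too close to the centre for that unit.

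Unequal arms within a site or country are to be expected:

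- The example range for n starts at 1, where a difference of one or two subjects is a large ratio.
- The factors visibly tagged as stratification factors in SAP 8.1.5 are region and baseline time to first prodromal symptom, not site.
- Protocol 11.5 randomizes one subset 1:2 to placebo or a single active dose, which unbalances the dose-placebo comparisons.

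At stake is the reading of an exploratory display. A site may look outlying by chance more often than the curves imply, or, under the other reading of the SD, less often.

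**Working it through.** **Inputs.** The limit formula, n and SD are from SAP 8.2.1 as above, with Z = 1.96. The planning values are from SAP 3.3: "standard deviation [SD] of 79.3 mins", "an absolute treatment difference of 57 mins between MT-7117" for one dose and "52 mins between MT-7117" for the other.

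**The plan's own figures.** The funnel paragraph gives a formula but no numerical result. The planning inputs are consistent with the stated effect sizes: 57/79.3 = 0.72 and 52/79.3 = 0.66. With equal arms the formula is exact. At 5 v 5 the half-width is 1.96 × 79.3 × sqrt(2/5) = 98.3 min on either formula, and 5.0% of homogeneous sites fall outside.

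**Step 1: ratio of planned to exact standard error.** With n = (n1+n2)/2,

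ratio = sqrt(2/n) / sqrt(1/n1 + 1/n2) = 2·sqrt(n1·n2)/(n1+n2).

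This is 1 only when n1 = n2. At 3 v 1 it is 2·sqrt(3)/4 = 0.866.

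**Step 2: chance of falling outside, within-arm SD.** The chance is 2 × [1 − Φ(1.96 × ratio)]. At 3 v 1, 1.96 × 0.866 = 1.697, which gives 9.0%.

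**Step 3: chance of falling outside if the SD ignores arm.** With the two groups of similar total size, the treatment difference d inflates the SD to sqrt(79.3² + d²/4):

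- d = 57: 84.3 min, factor k = 1.063
- d = 52: 83.5 min, factor k = 1.052

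The chance becomes 2 × [1 − Φ(1.96 × ratio × k)].

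| Arms | Ratio | Half-width at SD 79.3, planned → exact (min) | Outside, within-arm SD | Outside, SD ignoring arm (57 / 52 min) |
|---|---|---|---|---|
| equal (5 v 5) | 1.000 | 98.3 → 98.3 | 5.0% | 3.7% / 3.9% |
| 3 v 2 | 0.980 | 139.0 → 141.9 | 5.5% | 4.1% / 4.3% |
| 2 v 1 | 0.943 | 179.5 → 190.4 | 6.5% | 5.0% / 5.2% |
| 3 v 1 | 0.866 | 155.4 → 179.5 | 9.0% | 7.1% / 7.4% |
| 4 v 1 | 0.800 | 139.0 → 173.8 | 11.7% | 9.6% / 9.9% |

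If the SD ignores arm, the two effects cancel where ratio × k = 1. That is an imbalance of about 2.0:1 (57 min) or 1.9:1 (52 min).

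**Step 4: average over chance imbalance.** Each subject is assigned independently 1:1 to the two compared arms, and splits with an empty arm are dropped.

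| Subjects in the two arms | Within-arm SD | SD ignoring arm (57 / 52 min) |
|---|---|---|
| 3 | 6.5% | 5.0% / 5.2% |
| 4 | 7.3% | 5.7% / 5.9% |
| 6 | 7.5% | 5.9% / 6.2% |
| 10 | 6.7% | 5.2% / 5.4% |
| 20 | 5.7% | 4.3% / 4.5% |
| 30 | 5.4% | 4.1% / 4.3% |

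**The case against.** A reader might infer that the plot will flag too many sites wherever arms are unequal, at a rate well above 5%. The documents do not support that, for four reasons.

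- **Mild imbalance hardly matters.** At 3:2 the shortfall is 2%. Even with a within-arm SD, the rate averaged over chance splits stays at about 5.4–7.5%.
- **The SD wording may offset the error.** If the SD ignores arm, the limits are not too narrow until about 2:1. The averaged rate stays at about 6% or less and is below 5% for larger units such as countries.
- **There is no error rate to breach.** SAP 6.2 sets its level for formal tests: "all formal statistical tests of treatment effects will be done at two-sided significance level of 0.05". The funnel plot lies outside the H1–H12 sequence and has no decision attached. The 5% used here is only what the chosen normal quantile implies. The plot is also not the only look at consistency: Protocol 14.3.2.1 lists country among the subgroups for the primary endpoint.
- **The number of affected sites is unknown.** Neither the number of sites nor their arm sizes are given, and the allocation text is partly redacted.

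All four stand, and they limit the weight of the point. They do not remove it. The curves carry a standard error label that the formula does not meet at unequal arms. The possible offset from the SD does not repair this, because it makes the limits too wide at balanced sites while leaving them too narrow from about 3:1. One may also say that a single pair of curves indexed by average arm size is a fair simplification for a visual display. The harmonic mean keeps the same single pair of curves and changes only where each point is placed.

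**Conclusion.** The formula error is certain and its consequence is modest. For a given SD, the limits understate the standard error by 2%, 6%, 13% and 20% at 3:2, 2:1, 3:1 and 4:1. This becomes material at about 3:1 or beyond, which is plausible only at small sites. The undefined SD adds a second uncertainty of 5–6% in the width, in the opposite direction.

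The percentages assume normally distributed site means, no true heterogeneity between sites, and the SD and overall difference treated as known. The half-widths in minutes and the figures for an SD that ignores arm also rest on the planning values of SAP 3.3. The count of extra points outside the curves cannot be derived. No confirmatory result depends on the plot, so this is a minor improvement.

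**What to change.** In the funnel plot paragraph of SAP 8.2.1, make two changes together:

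1. Define n for each site and country as the harmonic mean arm size, 2·n1·n2/(n1+n2). Equivalently, replace sqrt(2/n) by sqrt(1/n1 + 1/n2).
2. State that the SD is pooled within arm.

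Under the assumptions above this gives 5.0% outside at every split. Neither change is enough alone. A within-arm SD with the average n gives the within-arm columns of the tables. A harmonic n with an SD that ignores arm leaves 3.7–3.9% outside at every split.

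The cost is one line in the SAP and in the program. No new data are needed and the confirmatory analyses are untouched.
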